For safety evaluation, hematology tests (white blood cell [WBC], neutrophil, lymphocyte, monocyte, eosinophil, basophil, red blood cell [RBC], hemoglobin [Hgb], hematocrit [Hct], mean corpuscular volume [MCV], mean corpuscular hemoglobin [MCH], mean corpuscular hemoglobin concentration [MCHC], platelet, erythrocyte sedimentation rate [ESR]), clinical chemical tests (T-protein, albumin, T-bilirubin, aminotransferase [ALT], aspartate aminotransferase [AST], *r*-glutamyl transpeptidase [GTP], blood urea nitrogen [BUN], creatinine), and immunologic tests (C-reactive protein [CRP]) will be performed before and after treatment for both groups to compare the incidence of adverse events.

Adverse events refer to undesirable and unintended signs, symptoms, or diseases that occur after the procedure, including events that may not be caused by the procedure. In this study, data regarding adverse events are collected based on patients' reports and investigators' observations. Further, we will analyze the incidence of adverse events, abnormal laboratory parameters, and serious adverse events suspected to be related to the treatment. The causality between the treatment and adverse events will be assessed using a 6-point scale following the World Health Organization-Uppsala Monitoring Centre causality assessment system (1, definitely related; 2, probably related; 3, possibly related; 4, probably not related; 5, definitely not related; and 6, unknown). The severity of all adverse events will be classified into three categories based on the Spilker classification: Mild (1), treatment not required without marked hindrance of normal everyday life (function); Moderate (2); significantly hinders normal

everyday life (function) with possible treatment being required and subsequent treatment; Severe (3): serious adverse event requiring advanced treatment and leaving sequelae.

Sample Size Calculation

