A pilot study was conducted to compare the effectiveness of pharmacopuncture and physiotherapy in patients with chronic LBP. The between-group difference in the mean reduction of the NRS score for LBP was 1.37 ± 1.94 at the primary endpoint, which is immediately after the 5-week treatment; further, Cohen's d was calculated as 0.71. The correlation between the baseline and endpoint was 0.53. Given a significance of 95% and power of 90%, the sample size was calculated to be 64. Considering a 30% withdrawal rate and the recruitment of participants from four facilities, we aim to recruit 100 patients.

Recruitment

Participants will be recruited using a press release, advertisement posters at the clinical trial facility, and online recruitment sites.

Randomization and Allocation Concealment

A statistician will randomize patients into two groups at the same ratio (50 persons for each) using a randomization table on R studio 1.1.463 (© 2009-2018 R Studio, Inc.). The random sequence will be performed using block randomization; further, the size of each block will be randomly set to 2 or 4. The randomization results will be placed in a sealed opaque envelope and stored in a double-locked cabinet by a third person not involved in the study. The coordinator at each study facility will open the envelope for group allocation. Only participants who provide an ICF will be randomly assigned. The randomization number assigned to each participant will be recorded in the electronic medical record.

Blinding

Since blinding the practitioner administering the treatment and the participants is impossible due to the nature of the intervention, only the outcome assessors will be blinded. Outcome-assessors not involved in the procedure and blinded from the group allocation will perform the assessment before the procedure in an isolated space.

Data Collection and Management

We will use an e-CRF using the Internet-based Clinical Research and Trial management system (iCReaT). The principal investigator will train the outcome assessors and investigators of each facility on the standard operating procedure (SOP) as a reference for the study procedures, including writing a CRF and entering data. A query will be issued for a range check of data values. Data entered into the e-CRF will be cleaned and locked to prevent access by investigators other than the one in charge of data management.

Statistical Methods

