We will perform both intention-to-treat (ITT) and per-protocol (PP) analyses, with ITT as the primary analysis. For the PP analysis, we will include participants who complete at least seven treatment sessions over 5 weeks. Missing data will be handled by multiple imputation (MI) for analysis of covariance (ANCOVA) and comparison of area under the curve (AUC), as well as

the mixed model for repeated measures for the linear mixed model. For survival analysis, outcomes after the missing time point will be censored. For sensitivity analysis, the last observation carried forward (LOCF) will be used for missing data imputation; further, the normality of distribution will be tested. Nonparametric data will be analyzed using the Wilcoxon-rank sum test. Sociodemographic characteristics and treatment expectancy of the participants will be assessed according to the group. Continuous variables will be presented as mean (SD) or median (quartile), with between-group differences being analyzed using Student's t-test or Wilcoxon-rank sum test, depending on their distribution. Categorical variables will be presented as frequency (%) and analyzed with the chi-square test or Fisher's exact test.

The study endpoints are the differences in the extent of changes in continuous outcomes (NRS, VAS, NDI, NPQ, EQ- 5D-5L, SF-12) at each time point from the baseline. As the primary analysis, we will use a linear mixed model with the covariant factors significantly different from the baseline as covariates and the group as the fixed factor. Next, ANCOVA will be performed on sets processed by MI and LOCF.

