To compare the total difference in each outcome within a certain period (treatment period and total study period), the AUC will be calculated for each time point after randomization and compared using Student's t-test. Further, the proportion of patients whose NRS and VAS scores dropped by > 50% from the baseline values will be compared at each time point. The time from randomization to lumbar recovery, which was defined as > 50% reduction in the pain indices, will be compared using Kaplan-Meier survival analysis. Further, the curves will be compared using the Log rank test. Additionally, hazard ratios will be compared using the Cox proportional hazard model. The significance level will be set at 0.05 for all analyses. All statistical analyses will be performed using the SAS 9.4 (© SAS Institute, Inc., Cary, NC, USA) or R studio 1.1.463 (© 2009-2018 RStudio, Inc.) software. Statistical significance will be set at $p < 0.05$.

In case the superiority test fails, a non-inferiority test will be performed. The non-inferiority margin will be set to -1 (NRS), which represents half of the minimal clinically important difference. Pharmacopuncture will be considered non-inferior to physiotherapy if the lower bound of the 95% confidence interval (CI) of the between-group difference of the NRS score reduction does not exceed the non-inferiority margin.

Data Monitoring

The monitoring staff will supervise the clinical trial process, as well as periodically review and confirm whether the study is performed and recorded according to the protocol, SOP, clinical trial management standards, and applicable regulations. The clinical trial will be monitored by the monitoring staff of each clinical trial facility and the sponsor institution using periodic visits and phone calls. At the monitoring visits, the monitoring staff will check the original participant records and data storage (study files). Further, they will inspect the clinical trial procedure and discuss any problems with the investigators.

In case of unexpected or unacceptable risks to participants or occurrence of serious adverse events related to pharmacopuncture or physiotherapy in $\geq 25\%$ of the participants, the clinical trial may be paused. The analysis will be only accessed by the statistician and principal investigator; additionally, the final decision to terminate the study will be made by the principal

investigator

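### The 23 blood parameters are to be compared only by the incidence of abnormal results; abnormal is not defined relative to the pre-treatment value, and no analysis of the measured values is planned

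*Combined protocol and SAP*

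**What the plan says.** The Adverse Events section lists 14 haematology tests, 8 chemistry tests and CRP, which makes 23 parameters. They "will be performed before and after treatment for both groups to compare the incidence of adverse events". The analysis statement is that "we will analyze the incidence of adverse events, abnormal laboratory parameters, and serious adverse events suspected to be related to the treatment". Adverse events are defined as "undesirable and unintended signs, symptoms, or diseases that occur after the procedure", whether or not the procedure caused them.

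The section gives no reference limits, no definition of an abnormal parameter, no rule for a value already out of range before treatment, and no shift table. It does not say whether incidence is counted per parameter or per participant.

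Statistical Methods defines the endpoints as "differences in the extent of changes in continuous outcomes (NRS, VAS, NDI, NPQ, EQ- 5D-5L, SF-12) at each time point from the baseline". Laboratory values are not in that list. No test is assigned to laboratory data. The nearest text is "Categorical variables will be presented as frequency (%) and analyzed with the chi-square test" or Fisher's exact test, and it sits in the description of sociodemographic characteristics and treatment expectancy. For error control, "The significance level will be set at 0.05 for all analyses".

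**The concern.** Safety is in the trial's title. The other adverse event data come from patient reports and investigator observation, and neither participants nor practitioners are blinded. The blood tests are therefore the only objective safety measurement in the plan.

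Two things can go wrong with the analysis as written. First, two statisticians could build different tables from the same data: one counting every out-of-range post-treatment result, the other only new ones. Second, a systematic shift in a liver, renal or inflammatory marker that stays mostly within range adds almost nothing to a count of abnormal results. A report of no difference in abnormal parameters would then read as reassurance that the data were hardly able to give.

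**Working it through.** **Inputs from the documents.** 23 parameters (14 + 8 + 1); "randomize patients into two groups at the same ratio (50 persons for each"); 30% withdrawal, so 50 × 0.70 = 35 per arm with post-treatment bloods if withdrawal is as planned; alpha 0.05, taken as two-sided because sidedness is not stated.

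**Assumptions.** The documents give no laboratory rates, SDs or correlations. I assume normally distributed values, a reference range covering the central 95%, and pre/post correlation r of 0.5 to 0.7.

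**The plan's own figure.** The only stated sample size is for the NRS. With d = 1.37/1.94 = 0.706 and r = 0.53, the baseline-adjusted effect is 0.706/√(1 − 0.53²) = 0.833. A noncentral t calculation at 90% power gives 32 per arm, 64 in total, which matches the plan. Then 64/0.70 = 91.4, rounded up to 92, and the plan recruits 100. The NRS sample size is thus reproduced by a calculation that uses the baseline correlation. No figure is given for any laboratory comparison.

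**Abnormal rates under a mean shift of s SD.** Control 5.0%; shifted arm 1 − Φ(1.96 − s) + Φ(−1.96 − s). For s = 0.5 this is 7.9%.

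**Power.** Fisher's test: exact binomial enumeration. ANCOVA: noncentral t with noncentrality s/√(1 − r²) × √(n/2) and 2n − 3 degrees of freedom. For s = 0.5 and n = 35, the noncentrality is 0.577 × 4.183 = 2.42 (r = 0.5) or 0.700 × 4.183 = 2.93 (r = 0.7).

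| Per arm | Shift | Abnormal rates | Fisher | ANCOVA, r = 0.5 to 0.7 |
|---|---|---|---|---|
| 35 | 0.5 SD | 5.0% vs 7.9% | 1% | 66% to 82% |
| 35 | 0.7 SD | 5.0% vs 10.8% | 4% | 92% to 98% |
| 35 | 1.0 SD | 5.0% vs 17.0% | 20% | over 99% |
| 50 | 0.5 SD | 5.0% vs 7.9% | 3% | 82% to 93% |
| 50 | 1.0 SD | 5.0% vs 17.0% | 35% | over 99% |

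**Sensitivity to the test and the limit.** Fisher's test is conservative at these rates. By the normal approximation, 5.0% vs 7.9% at 35 per arm gives z = 0.0291/√((0.0475 + 0.0728)/35) = 0.50, and power Φ(0.50 − 1.96), about 7%; at 50 per arm it is about 9%. If only an upper limit at the 97.5th percentile matters, the rates are 2.5% vs 7.2%: Fisher 2% (35) or 5% (50), normal approximation 15% or 19%. The gap to ANCOVA stays wide in every case.

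**Where the loss comes from.** At 35 per arm and 0.5 SD, a t-test on post-treatment values alone, with no baseline, has 54% power. Counting only new abnormalities leaves Fisher power at no more than about 2%. Most of the loss is therefore due to dichotomising; baseline adjustment adds the step from 54% to 66% to 82%.

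**Flags already present.** With no treatment effect, the share of post-treatment abnormal values that were already abnormal before treatment is about 19% (r = 0.5), 33% (r = 0.7) or 59% (r = 0.9). Whether these count as incident is what the plan leaves open.

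**Differences stated directly as rates.** Exact Fisher power, 50 (35) per arm: 2% vs 6%, 3% (1%); 2% vs 10%, 19% (7%); 5% vs 15%, 24% (14%); 2% vs 20%, 78% (53%); 2% vs 25%, 93% (76%). With no abnormal values in an arm, the one-sided 95% upper bound is 1 − 0.05^(1/n): 5.8% (8.2%).

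**Multiplicity.** 23 × 0.05 = 1.15 false positives expected; 1 − 0.95²³ = 69% chance of at least one if the parameters are independent.

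**The case against.** A reader might infer that the plan discards the pre-treatment result. The documents do not say so. The pre-treatment sample is named as part of the comparison, incidence ordinarily means new occurrence, and adverse events are those arising after the procedure. Counting only new abnormalities is at least as natural a reading. What stands is that the text does not settle it.

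A reader might also infer that the trial has almost no chance of detecting any laboratory harm. That is too broad. The 1% figure belongs to a 0.5 SD mean shift, which no document calls a harm, and large excesses of abnormal results have reasonable power. For rare abnormalities the limit is a sample size set on the NRS, and neither ANCOVA nor a shift table changes that.

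The endpoint list is weak evidence of intent. It names NDI and NPQ, which are not outcomes of this trial, and omits ODI and RMDQ, which are. The absence of laboratory values shows that no analysis is specified, not that one was considered and rejected.

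The power contrast also rests on normality, whereas transaminases, GTP and CRP may well be skewed; the proposed log scale addresses that only in part.

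Finally, arguing from power and then labelling the estimates descriptive looks inconsistent. It is not: power here measures the information lost. At 35 per arm the 95% CI for the adjusted difference has half-width 2.00 × √((1 − r²) × 2/35), that is ±0.41 SD (r = 0.5) or ±0.34 SD (r = 0.7). A reader can judge a shift from that interval without a significance test.

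**Conclusion.** The point holds as a gap in the laboratory analysis. The plan collects paired measurements of 23 parameters, commits only to an incidence of abnormal results, leaves abnormal undefined relative to the pre-treatment value, and plans nothing for the measured values. Under the stated assumptions, the yes/no comparison would probably miss small to moderate mean shifts that the same data could show. The exact percentages depend on the assumed reference range, correlation and normality; the direction and rough size of the contrast do not change over the range examined. The verdict does not extend to a claim that baseline is ignored by design or that laboratory harms in general would go undetected. This is more than missing detail, because a clearly better analysis is available from data already being collected, but it does not touch the primary endpoint.

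**What to change.** Add to Statistical Methods, before the data are analysed:

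- For each parameter, estimate the between-arm difference in the post-treatment value by ANCOVA on the pre-treatment value, on the log scale where the distribution is skewed, and report it with its 95% CI.
- State the reference limits used. Count as incident only a parameter that was normal before and abnormal after treatment, and present this as a per-parameter shift table by arm.
- Label the 23 estimates descriptive, with no claim of safety or harm resting on a single p-value.

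The cost is SAP wording and one further table from data already collected. The downside is that about one of the 23 comparisons will reach p < 0.05 by chance, hence the label. The change does not improve the trial's ability to detect rare individual abnormalities, and the report should say so.

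### Grade 3 (Severe) requires a serious event that leaves sequelae, so an intense reaction that resolves cannot be graded Severe, and serious is nowhere defined on its own

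*Combined protocol and SAP*

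**What the plan says.** Under Adverse Events, one scale covers everything: "The severity of all adverse events will be classified into three categories based on the Spilker classification". Mild is an event that needs no treatment and does not markedly disturb daily life. Moderate is an event that "significantly hinders normal" "everyday life (function) with possible treatment being required and subsequent treatment" (one definition, split by a page break). The top grade is "Severe (3): serious adverse event requiring advanced treatment and leaving sequelae".

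The word serious has two other uses that matter here. The same section lists, among the items to be analysed, "abnormal laboratory parameters, and serious adverse events suspected to be related to the treatment". Under Data Monitoring the pause rule reads "In case of unexpected or unacceptable risks to participants or occurrence of serious adverse events related to pharmacopuncture or physiotherapy in" at least 25% "of the participants, the clinical trial may be paused". Neither place says what makes an event serious, and no other section does.

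**The concern.** Severity describes how intense an event is. Seriousness is a regulatory classification, and sequelae are an outcome known only later. Grade 3 asks for all of them at once. A reaction after injection that needs emergency care or admission and then clears completely has left no sequelae, so it fails grade 3 however intense it was.

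Two things are at stake. First, the severity table cannot show intense events that resolved, in a trial whose title names safety alongside effectiveness. Second, the grade 3 line is the only descriptive text attached to a serious event. With four facilities classifying events from patient reports and investigator observation, one site may treat that line as the definition of a serious adverse event while another uses a regulatory definition. The serious-event count would then not mean the same thing at each site.

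**Working it through.** The plan states no figure that depends on this wording, so there is none to reproduce. The check is mainly textual.

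**Step 1. Apply the three grades as written to four hypothetical events.**

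| Event | Mild | Moderate | Severe |
|---|---|---|---|
| Disturbs daily life, ordinary treatment, resolves | no | yes | no |
| Intense, advanced treatment, serious, resolves fully | no: treatment needed | nearest, but describes only possible treatment | no: no sequelae |
| Intense, advanced treatment, serious, leaves sequelae | no | exceeded | yes |
| Intense and disabling for a time, not serious on any usual criterion | no | nearest | no: not serious |

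Rows 2 and 4 show the defect. Both are intense, neither can be Severe, and both drift towards the grade in row 1. This follows from the wording alone and needs no assumption about how sites behave.

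**Step 2. Does the wording reach the serious-event count?** The grade 3 line defines Severe by means of serious, not the reverse. The pause rule refers to serious adverse events, not to grade 3. Read grammatically, a resolved serious event still counts. It drops out only if a site takes the grade 3 line as its definition of serious. Nothing says to do so, and nothing supplies another definition.

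**Step 3. Which part of the pause rule could be affected?** There are two limbs. The first, unexpected or unacceptable risks, carries no seriousness label and no count. The second needs related serious events in at least 25% of participants. Only the second can depend on how serious is read.

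**Step 4. Illustration for the second limb.** Inputs: 100 planned participants (Study Design and Setting; Sample Size Calculation) and the 25% threshold (Data Monitoring). Threshold count: 0.25 × 100 = 25, taking all enrolled participants as the denominator. Assumptions not in the documents: a true proportion p of participants with a related serious event, independence between participants, and half of such events leaving sequelae. Formula: P(X ≥ 25) with X ~ Binomial(100, p), replacing p by p/2 if only events with sequelae are counted.

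| Assumed true p | All related serious events counted | Only the half with sequelae counted |
|---|---|---|
| 10% | 0.00001 | below 0.00001 (p/2 = 5%) |
| 20% | 0.13 | 0.00001 (p/2 = 10%) |
| 30% | 0.886 | 0.006 (p/2 = 15%) |

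The reading of serious changes this limb materially only if related serious events are very common, at roughly 20% of participants or more. At lower rates the limb would almost never be met under either reading.

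**The case against.** The strongest reply has four parts.

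- **The pause rule is largely untouched.** A reader might infer that a dangerous reaction which resolves falls outside the pause rule, or that the 25% limb needs 25 participants left with sequelae. The documents support neither. The rule does not use the severity grade, its first limb needs no label or count, and resolved serious events drop out of the second limb only on a reading that the text does not state. This part stands.
- **The understatement cannot be quantified.** A reader might infer that every resolved serious event becomes Moderate, so that the Severe count is some fixed fraction of the truth. That would need a resolution rate the documents do not give. It would also treat every serious event as truly severe, which repeats the confusion at issue. Nor is Moderate certain: an event needing advanced treatment fits neither upper grade well. This part stands.
- **Timing does no harm.** Grade 3 cannot be settled until sequelae are known, but no section ties an action to the grade, so nothing the protocol requires is delayed. This part stands.
- **Other provisions cover the gap.** Related serious events are analysed separately from severity, the facilities are trained on an SOP that covers CRF completion, and monitoring is against applicable regulations. The e-CRF and SOP are not in the documents, so a seriousness field may already exist. This limits the consequence. It does not repair the grade 3 wording, and no section says that the SOP or the regulations supply the definition of serious.

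**Conclusion.** The point holds for the severity scale. As written, grade 3 excludes intense events that resolve and intense events that are not serious, so the severity table can understate harm. This is a stated rule that misclassifies events, not merely missing detail.

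For the serious-event analysis and the 25% limb, the finding is only that an undefined term leaves room for sites to differ. The limb on unexpected or unacceptable risks is not affected.

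No size can be put on the understatement from the documents. The probabilities shown for the 25% limb rest on assumed event rates and an assumed one-half share with sequelae, and they indicate little practical effect unless related serious events are very frequent. The plan should be corrected, but the case for doing so rests on the severity table and on consistent classification, not on a failure of the pause rule.

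**What to change.** 1. In Adverse Events, grade severity by intensity and functional impact only. Remove the references to a serious adverse event and to sequelae from grade 3.
2. Record seriousness as a separate yes/no item for each adverse event, using the definition in the applicable regulations to which Data Monitoring already refers, and say so in the protocol.
3. Reconcile Adverse Events with Data Monitoring by stating that both the serious-event analysis and the 25% limb use that item and not the severity grade.

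The cost is a few lines of protocol text, a matching line in the site training and, if it is not already there, one e-CRF item. Somewhat more events may be labelled severe than under the present wording. The change alters no treatment and leaves the pause threshold as it is.

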Effectiveness and Safety of Pharmacopuncture Therapy for Chronic Low Back Pain: Study protocol

Protocol ID : JS-CT-2021-02

Clinical trials : NCT04833309

Document Date : September 30, 2021

Study Design and Setting

This two-armed, parallel, multi-center RCT will competitively recruit 100 patients in the Jaseng Hospital of Korean Medicine, Daejeon Jaseng Hospital of Korean Medicine, Bucheon Jaseng Hospital of Korean Medicine, and Haeundae Jaseng Hospital of Korean Medicine. The study protocol was approved by the Institutional Review Board (IRB) of Jaseng Hospital of Korean Medicine before participant recruitment (JASENG 2021-02-012, JASENG 2021-02-013, JASENG 2021-02-014, JASENG 2021-02-032). Additionally, the study protocol will be registered with Clinicaltrials. gov (NCT04833309) and Clinical Research Information Service (KCT0006088) and continuously updated.

Inclusion/Exclusion Criteria

Inclusion Criteria

- LBP onset \geq 6 months
- Numeric rating scale (NRS) score of LBP \geq 5
- Age 19–70 years
- Signing of the ICF to participate in the clinical trial

Exclusion Criteria

- Diagnosis of a serious disease that may cause LBP (eg, spinal metastasis of tumor, acute fracture, spinal dislocation)
- Progressive neurological defects or severe neurological symptoms
- Pain is caused by soft tissue disease rather than the spine (eg, tumor, fibromyalgia, rheumatic arthritis, gout)
- Other chronic diseases that may hinder the interpretation of treatment effects or outcomes (eg, stroke, myocardial infarction, renal disease, diabetic neuropathy, dementia, epilepsy)
- Current use of steroids, immunosuppressants, antipsychotic agents, or other drugs that may affect study outcomes
- Contraindications for pharmacopuncture, including hemorrhagic diseases, anticoagulant usage, severe diabetes mellitus with risk of infection
- Use of drugs that may affect pain, including non-steroidal anti-inflammatory drugs, or pharmacopuncture therapy within the previous week
- Pregnant or breastfeeding women, as well as women planning to conceive
- Lumbar surgery in the previous three months
- Less than one month since participating in another clinical trial or planning to participate in another clinical trial during the study period or follow-up period within 6 months upon enrolment
- Declining to sign a consent form to participate

- Other disqualifications as determined by the investigators

Interventions

Experimental Group: Pharmacopuncture Therapy

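### The 90% power stated for 64 evaluable patients depends on a baseline adjustment that the primary model does not prespecify; taking 1.94 as the SD of the reduction and no adjustment, 86-88 are needed

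*Combined protocol and SAP*

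**What the plan says.** The section Sample Size Calculation rests on a pilot comparison of the two treatments. It reports that the between-group "difference in the mean reduction of the NRS score for LBP was 1.37 ± 1.94" immediately after the five-week treatment, and that "Cohen's d was calculated as 0.71". It adds: "The correlation between the baseline and endpoint was 0.53". It then concludes: "Given a significance of 95% and power of 90%, the sample size was calculated to be 64". Allowing for 30% withdrawal and four sites, the target is 100. No formula, test or sidedness is given, and the pilot's separate baseline and endpoint SDs are not reported.

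Three other places bear on this:

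- Statistical Methods defines the endpoints as changes from baseline. The primary linear mixed model has group as the fixed factor, and its covariates depend on a significance finding at baseline. Baseline NRS is not named. ANCOVA comes afterwards, on imputed data sets.
- Statistical Methods also says: "The significance level will be set at 0.05 for all analyses".
- Inclusion Criteria requires a "Numeric rating scale (NRS) score of LBP" of at least 5, on a scale that Outcome defines as 0-10.

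**The concern.** Since 1.37/1.94 = 0.706, the 1.94 is used as the SD of the reduction, which is also how the sentence labels it. A change-score SD already reflects the baseline-endpoint correlation. Using the correlation again to reduce the sample size is justified only if the primary analysis adjusts for baseline, and then only by a factor that depends on the ratio of the baseline SD to the endpoint SD. The plan neither commits to that adjustment nor gives that ratio.

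If the reduction from the correlation is not earned, the type II error under the assumed effect is larger than the planned 10%. A failed superiority test leads to the non-inferiority test, so the chance of reaching that fallback would be understated. A reader of a null result would also judge it against a power that the design may not have had.

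**Working it through.** **Inputs.** Difference δ = 1.37, SD 1.94, r = 0.53, power 90% and 30% withdrawal (Sample Size Calculation); significance level 0.05 (Statistical Methods); equal allocation (Randomization and Allocation Concealment). Two-sided testing is my assumption.

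**Formula.** Normal approximation, per arm: n = 2(1.960 + 1.282)² × f / d², where f is the factor applied to the variance. With d = 1.37/1.94 this is 42.14f; with the stated d = 0.71 it is 41.69f. Figures marked t use the noncentral t distribution, with one covariate where baseline is adjusted for.

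**Reproducing 64.**

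- No use of r (f = 1): 42.14, so 43 per arm, 86 in total (88 with t). Not 64.
- f = 1 - 0.53² = 0.719, unrounded d: 30.30, so 31 per arm, 62 in total; with t, exactly 64 (90.6% power).
- f = (1 + 0.53)/2 = 0.765, d = 0.71: 31.89, so 32 per arm, exactly 64 (90.1%, normal). With unrounded d: 32.24, so 66 (68 with t).
- Unadjusted at 80% power also gives 64 (normal), but the text states 90%.
- Unadjusted, one-sided 5%, 90% power gives 70 (72 with t).

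So at the stated 90% power 64 uses the correlation, but the documents do not show by which factor.

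**The factor that applies.** Let k = baseline SD / endpoint SD. If 1.94 is the SD of the reduction, the ratio of the baseline-adjusted residual variance to the change variance is

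f = (1 - r²) / (1 + k² - 2rk).

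At k = 1 this is (1 + r)/2 = 0.765. At k = r = 0.53 it is 1.00, so adjustment gains nothing over the change score. It equals 0.719 only at k = 1.06 (or in the limit k = 0). Applying 1 - r² directly to a change variance therefore credits the baseline twice; that factor belongs to an endpoint-score variance.

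**How large can k be?** With equal SDs s, the change SD is s√(2(1 - r)), so s = 1.94/√0.94 = 2.00. The entry rule limits baseline to 5-10. An even spread over those six integers has SD √(35/12) = 1.71. For each assumed baseline SD s0, the endpoint SD s1 solves s1² - 2(0.53)s0·s1 + s0² = 1.94², and the residual SD is s1√(1 - 0.53²).

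| Analysis and assumed baseline SD | f | N for 90% | Power at 64 | Power at 70 |
|---|---|---|---|---|
| No baseline adjustment | 1.00 | 86 (t: 88) | 80.6% (t: 79.4%) | 84.0% (t: 83.0%) |
| Adjusted, 1.0 | 0.99 | 86 (t) | 79.8% (t) | 83.4% (t) |
| Adjusted, 1.2 | 1.00 | 88 (t) | 79.4% (t) | 82.9% (t) |
| Adjusted, 1.5 | 0.98 | 86 (t) | 80.4% (t) | 83.8% (t) |
| Adjusted, 1.71 | 0.92 | 80 (t) | 82.5% (t) | 85.8% (t) |
| Adjusted, 2.0 (equal SDs) | 0.765 | 66 (t: 68) | 89.8% (t: 88.8%) | 92.2% (t: 91.4%) |

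The 70 is 100 × 0.7. With adjustment, 90% at 70 requires k of at least about 0.91 (normal) or 0.95 (t). At 64 it requires k of about 1.04 (t).

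**If 1.94 is the endpoint SD.** The factor 0.719 is then correct for a baseline-adjusted analysis, and 64 gives 90.6%. For an unadjusted change score with equal SDs, the change SD would be 1.94√0.94 = 1.88, and 80 (t: 82) would be needed.

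**The case against.** A reader might infer that the sponsor multiplied the change variance by 1 - r² and so made a definite arithmetic error. The documents do not support that. No formula is given, and the legitimate equal-SD factor with d rounded to 0.71 also gives exactly 64. With that rounded d, 1 - r² gives 60 (t: 62). Double crediting of the baseline is one possible explanation, not a demonstrated one.

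The 1.94 may also be an endpoint SD, since quoting a baseline-endpoint correlation fits ANCOVA sizing. That reading would save 64 for an adjusted analysis, but it contradicts the label in the text, so an edit is needed either way.

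The narrow-baseline argument combines pilot figures with this trial's entry rule. The pilot's own entry rule and SDs are not given, so the 1.0-1.71 range is a sensitivity range and not a finding.

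Taking 70 as the analysed number may be pessimistic. The primary analysis is ITT with a repeated-measures mixed model, so patients who withdraw after some post-baseline visits still contribute. If all 100 contributed in full, even the unadjusted analysis would have 93.8% power. That is an upper bound: patients without the five-week value do not contribute a full observation at the primary time point.

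These points limit the claim. They do not restore 90% at 64 for the primary model as written, with 1.94 as labelled.

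**Conclusion.** The point holds in conditional form. With 1.94 as the SD of the reduction and two-sided 5%, the stated 90% at 64 is not delivered by a primary model without baseline NRS: power is 79-81% at 64 and 83-84% at 70. If baseline is adjusted for and its SD is 1.0-1.71, power is about 79-83% at 64 and 83-86% at 70. If the baseline and endpoint SDs are equal, the shortfall at 64 is only about 0.2 to 1.1 percentage points, and 70 completers give 91-92%.

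It would go too far to say that the trial falls below 90% at its expected 70 completers. That follows if baseline is not adjusted for, or if the baseline SD is below about 0.91-0.95 of the endpoint SD. The first is left open by the plan; the second is plausible under the entry rule but undocumented. All these figures assume that the pilot's 1.94 and 0.53 carry over to this trial.

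**What to change.** In Sample Size Calculation, state the formula, the sidedness, whether 1.94 is the SD of the reduction or of the endpoint score, and the pilot's baseline and endpoint SDs. Then match the calculation to the primary model:

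- If baseline NRS is prespecified as a covariate in that model, recalculate from the pilot's baseline-adjusted residual SD.
- If it is not, use the reduction SD of 1.94 with no correlation factor, which gives 86-88.

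Replace 64 by the result and restate the power at the 70 expected completers. If 1.94 proves to be the endpoint SD and the analysis is baseline-adjusted, keep 64 and correct the label. Keep the target of 100.

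The cost is one rewritten paragraph and a consistent statement on baseline NRS in Statistical Methods. No extra patients are asked for. The downside is that the stated power will probably become less favourable: holding 90% after 30% withdrawal would take 98 recruits if 68 are needed (68/0.7), but 115 to 126 if 80 to 88 are needed (80/0.7 to 88/0.7).
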